5.1. Summary of Study Design

Study ITRM is a Phase 3, prospective, randomized, double-blind, outpatient, multinational, multicenter 3-treatment group, parallel, active-controlled study in patients with type 1 diabetes mellitus (T1D) currently using a multiple daily injections regimen. For patients in the 2 double-blind treatment groups, the study includes a 1-week screening period and an 8-week lead-in period followed by a 52-week treatment period and a 4-week safety follow-up period. For patients in the open-label treatment group who are not in Japan, the treatment period will end after 26 weeks, which will be followed by a 4-week safety follow-up period. Open-label treatment group patients in Japan will follow the same schedule as the double-blind treatment groups. [Figure 5.1](#) illustrates the study design.

[figure not shown]
All patients who complete the 4-week safety follow-up visit (Visit 801) and have treatment-emergent anti-insulin lispro antibodies response that have not returned to the pre-specified baseline range (Visit 2) will be asked to participate in follow-up to monitor insulin lispro antibody levels for up to 26 weeks after Visit 801. The follow-up consists of Visits 802 and 803.

5.2. Determination of Sample Size

Assuming a noninferiority margin (NIM) of 0.4%, no true difference between treatment arms, and a standard deviation (SD) of 1.1%, approximately 371 completers in each double-blind treatment group will provide at least 99% power to show noninferiority between LY900014 and insulin lispro in change from baseline to 26 weeks in hemoglobin A1c (HbA1c) using the upper limit of a 2-sided 95% confidence interval (CI) (LY900014 – insulin lispro). Assuming a 15% dropout rate for 26 weeks, 4:4:3 randomization ratio (LY900014, insulin lispro, and LY900014+20), approximately 1199 patients will need to be randomized. This sample size also has 95% power to show noninferiority between LY900014 and insulin lispro using a 0.3% NIM at 26 weeks.

5.3. Method of Assignment to Treatment

Patients who meet all criteria for enrollment will be randomized to double-blind or open-label treatment at Visit 8. Assignment to treatment groups will be determined by a computer-generated random sequence using an interactive web-response system (IWRS). Patients will be randomized to double-blind LY900014, double-blind insulin lispro, or open-label LY900014+20 in a 4:4:3 ratio. Stratification will be by country, HbA1c stratum ($\leq 7.5\%$, $>7.5\%$ at Visit 7), type of basal insulin during the lead-in period (glargine U-100 or degludec U-100), and prandial insulin dosing plan at randomization (carbohydrate counting, pattern adjustment).

Abbreviation: T = telephone visit.

- a At Visit 2, patients on insulin glulisine or insulin aspart will be transferred to insulin lispro. The patients’ basal insulin regimen will be switched to insulin glargine U-100 (once or twice daily) or to insulin degludec U-100 once daily. At Visit 8, patients will be randomized to either premeal insulin lispro, premeal LY900014, or LY900014+20 and continue their basal insulin regimen.
- b Titrate basal insulin.
- c Titrate prandial insulin (insulin lispro or LY900014).
- d Patients will discontinue study insulins at Week 26 for the LY900014+20 open-label treatment group or Week 52 for the 2 blinded treatment groups.
- e Eligible patients will have visits at approximately 3-month intervals for up to 26 weeks after Visit 801 for follow-up of insulin lispro antibody levels.

Figure 5.1. Illustration of study design.

6. A Priori Statistical Methods

6.1. General Considerations

Statistical analysis of this study will be the responsibility of Eli Lilly and Company (hereafter Lilly). Any change to the data analysis methods described in the protocol will require an amendment ONLY if it changes a principal feature of the protocol. Any other change to the data analysis methods described in the protocol, and the justification for making the change, will be described in this SAP and/or in the clinical study report (CSR). Additional exploratory analyses will be conducted, as deemed appropriate.

Statistical analyses for the continuous glucose monitoring (CGM) addendum are provided in a separate SAP. Statistical analyses for Japan are described in [Appendix 2](#). Statistical analyses for the Maximum Extended Enrollment (MEE) Addendum are described in [Appendix 3](#).

For purposes of analysis, the following populations are defined in [Table 6.1](#):

Table 6.1. Patient Populations

Population	Description
Entered	All patients who give informed consent.
Enrolled	All patients who receive at least 1 dose of open-label insulin lispro in the 8-week lead-in period.
Randomized	All patients who are randomly assigned to study treatment at Visit 8. Treatment group will be defined on the basis of the treatment the patients are assigned.
Safety	All randomized patients who receive at least 1 dose of the randomly assigned investigational product (IP). Treatment group will be defined on the basis of the treatment the patients are assigned.
Completer	Patients included in the randomized population who have completed Week 26 of study treatment without permanent discontinuation of IP. Treatment group will be defined on the basis of the treatment the patients are assigned.
Per Protocol	Patients included in the randomized population who have completed Week 26 of study treatment without permanent discontinuation of IP and without significant protocol deviations through Week 26 that would significantly impact the primary objective. Treatment group will be defined on the basis of the treatment the patients actually receive.

Unless otherwise stated, the efficacy analyses will be conducted on the Randomized Population, and the safety analyses will be conducted on the Safety Population.

The primary analysis is for the treatment period through Week 26. The primary endpoint is the HbA1c measurement obtained at Week 26 (Visit 18). The measurement obtained at Week 52 (Visit 22) will be a secondary endpoint.

Unless otherwise noted, all tests of treatment effects will be conducted at a 2-sided alpha level of 0.05, and CIs will be calculated at 95%, 2-sided. All tests of interactions between treatment groups and other factors will be conducted at a 2-sided alpha level of 0.10.

The definitions of baseline and postbaseline for the efficacy and safety analyses depend on which analysis period is being used. The following analysis periods will be used:

- Lead-in Period – Visits 2-8
- 26-Week Treatment Period – from randomization to Week 26 prior to discontinuation of IP and from randomization to Week 26 (including all data regardless of IP use) – all treatment groups
- 26-Week Treatment Period and Safety Follow-Up Visit – from randomization to Visit 801 (including all data regardless of IP) – LY900014+20 treatment group excluding patients from Japan
- 52-Week Treatment Period - from randomization to Week 52 prior to discontinuation of IP and from randomization to Week 52 (including all data regardless of IP use) – double-blind treatment groups
- 52-Week Treatment Period and Safety Follow-Up Visit – from randomization to Visit 801 (including all data regardless of IP use) – double-blind treatment groups.

Patients randomly assigned to the LY900014+20 treatment group in Japan will remain in the study until Week 52 and subsequently will have the Safety Follow-Up Visit only after Week 52 for patients who complete the study.

The data on IP is defined based on the following rules:

- for data only measured at an office visit
 - MMTT postbaseline data will be considered as data on IP if the MMTT performance date is on or prior to the last IP dose date
 - Other postbaseline data (for example, vital signs, laboratory tests, and questionnaires) will be considered as data on IP if the measurement date is on or prior to the cutoff date defined as 14 days after the last IP dose date
- for data collected as running records with an exact date stamp such as adverse events (AEs) and diary entries where the dates of the measures were not tied with the date of an office visit, postbaseline data with dates \leq (last study drug dose date +1) will be considered as data on IP.

Table 6.2 describes the rules for determining the patient population, baseline and postbaseline observations for the different analysis periods.

For continuous measures, summary statistics will include sample size, mean, SD, median, minimum, and maximum for both the actual and the change from baseline measurements. Least-squares (LS) means and standard errors derived from the analysis models will also be displayed. Treatment comparisons will be displayed showing the treatment difference LS means and the 95% CIs for the treatment differences, along with the p-values for the treatment comparisons.

For categorical measures, summary statistics will include sample size, frequency, and percentages. Fisher’s exact test or Pearson’s chi-square test will be used for treatment comparisons.

For laboratory values, both conventional (CN) and Systeme International (SI) units will be presented. Therefore, both % and mmol/mol will be presented for HbA1c and both mg/dL and mmol/L will be presented for glucose measurements.

All baseline measures will be analyzed using an analysis of variance (ANOVA) model that has treatment as the model terms.

Table 6.2. Baseline and Postbaseline Definitions and Patient Population by Study Period and Type of Analysis

Study Period/Analysis	Patient Population	Baseline Observations	Postbaseline Observations
Lead-In Period			
TEAEs	All Enrolled Patients	Prior to first dose of open-label insulin lispro (or Visit 2 date if the dose date is missing)	The entire lead-in period after first dose of open-label insulin lispro and prior to the first dose of IP (or Visit 8 date if the dose date is missing)
Basal, prandial, and total insulin doses, and prandial/total insulin dose ratio	All Randomized Patients	Visit 2	Visits 3–8 prior to initiation of IP
Weight MMRM and ANCOVA	All Randomized Patients	Last of Visits 1-2	Visits 3–8 AND Last of Visits 3-8
26-Week Treatment Period (including Safety Follow-Up Visit where applicable)			
HbA1c MMRM and ANCOVA (efficacy estimand)	All Randomized Patients with a baseline and at least 1 postbaseline observation while on IP	Last of Visits 7-8	Visits 11, 13, 15, and 18 prior to discontinuation of IP AND Last of Visits 9-18 prior to discontinuation of IP

Baseline and Postbaseline Definitions and Patient Population by Study Period and Type of Analysis

Study Period/Analysis	Patient Population	Baseline Observations	Postbaseline Observations
HbA1c ANCOVA (ITT estimand)	All Randomized Patients with a baseline and at least 1 postbaseline observation	Last of Visits 7-8	Visit 18 regardless of IP use, with imputation for patients who discontinue the study prior to Visit 18
HbA1c categorical analyses longitudinal logistic regression and LOCF logistic regression	All Randomized Patients with a baseline and at least 1 postbaseline observation while on IP	Last of Visits 7-8	Visits 11, 13, 15, and 18 prior to discontinuation of IP AND Last of Visits 9-18 prior to discontinuation of IP
1-hr and 2-hr PPG and other MMTT variables (efficacy estimand)	All Randomized Patients with a postbaseline observation while on IP	Visit 8 prior to initiation of IP	Visit 18 prior to discontinuation of IP
1-hr and 2-hr PPG and other MMTT variables (ITT estimand)	All Randomized Patients with a postbaseline observation	Visit 8 prior to initiation of IP	Visit 18 regardless of IP use
10-point SMBG, basal, prandial, and total insulin doses, prandial/total insulin dose ratio	All Randomized Patients with a baseline and at least one postbaseline observation	Visit 8 prior to initiation of IP	Visits 11, 13, 15, and 18 prior to discontinuation of IP AND Last of Visits 9 to 18 prior to discontinuation of IP
1,5-AG	All Randomized Patients with a baseline and at least 1 postbaseline observation	Visit 8 prior to initiation of IP	Visits 11, 15, and 18 prior to discontinuation of IP AND Last of Visits 9-18 prior to discontinuation of IP
Health outcomes: ITSQ, CCI	All Randomized Patients with a baseline and a postbaseline observation	Last of Visits 1-8	Last of Visits 9-18 prior to discontinuation of IP
Safety Laboratory Tests (chemistry, hematology, lipids) – continuous analysis	All Patients in the Safety Population with a baseline and a postbaseline observation	Last of Visits 1-8	Visit 18 (planned) AND Last of Visits 9-18 (planned including early discontinuation), regardless of IP use
Safety Laboratory Tests (chemistry, hematology, lipids) – categorical analysis	All Patients in the Safety Population with a normal baseline (with respect to the direction being analyzed) and a postbaseline observation	Visits 1 -8 (including unplanned tests)	Visits 9 to 18 (including unplanned tests), regardless of IP use

Baseline and Postbaseline Definitions and Patient Population by Study Period and Type of Analysis

Study Period/Analysis	Patient Population	Baseline Observations	Postbaseline Observations
TEAEs	Safety Population	Prior to first dose of randomized IP (or Visit 8 date if missing) and after the first dose of open-label insulin lispro (or Visit 2 date if missing)	From first dose of randomized IP to last dose of randomized IP AND From first dose of randomized IP to Visit 18 or from first dose of randomized IP to Visit 801 (for LY900014+20 treatment group)
Hypoglycemia events	Safety Population	All Visits 2-8	All Visits 9-18 prior to discontinuation of IP
Weight and vital signs	All Patients in the Safety Population with a baseline and a postbaseline observation	Last of Visits 2-8	Visits 9-18 prior to discontinuation of IP AND Visits 9-18 regardless of IP use or Visits 9-801 for LY900014+20 treatment group
Anti-insulin lispro antibody	Safety Population	Visit 2	Visits 3-18 AND Visits 3-801 (for LY900014+20 treatment group), regardless of IP use
52-Week Treatment Period (including Safety Follow-Up Visit where applicable)			
HbA1c	All Randomized Patients in the Double-Blind Treatment Groups	Last of Visits 7-8	Visits 11, 13, 15, 18, 20, and 22 prior to discontinuation of IP AND Last of Visits 9-22 prior to discontinuation of IP
10-point SMBG, basal, prandial, and total insulin doses, prandial/total insulin dose ratio	All Randomized Patients in the Double-Blind Treatment Groups	Visit 8 prior to initiation of IP	Visits 11, 13, 15, 18, 20, and 22 prior to discontinuation of IP AND Last of Visits 9-22 prior to discontinuation of IP
1,5-AG	All Randomized Patients in the Double-Blind Treatment Groups	Visit 8 prior to initiation of IP	Visits 11, 15, 18, 20, and 22 prior to discontinuation of IP AND Last of Visits 9-22 prior to discontinuation of IP
Health outcomes: ITSQ CCI	All Randomized Patients in the Double-Blind Treatment Groups	Last of Visits 1-8	Last of Visits 9-22 prior to discontinuation of IP
Safety Laboratory Tests (chemistry, hematology, lipids) – continuous analysis	All Double-Blind Patients in the Safety Population with a baseline and a postbaseline observation	Last of Visits 1-8	Visit 22 (planned) AND Last of Visits 9-22 (planned including early discontinuation), regardless of IP use

Baseline and Postbaseline Definitions and Patient Population by Study Period and Type of Analysis

Study Period/Analysis	Patient Population	Baseline Observations	Postbaseline Observations
Safety Laboratory Tests (chemistry, hematology, lipids) – categorical analysis	All Double-Blind Patients in the Safety Population with a normal baseline (with respect to the direction being analyzed) and a postbaseline observation	Visits 1-8 (including unplanned tests)	Visits 9-22 (including unplanned tests) regardless of IP use.
TEAEs	All Double-Blind Patients in the Safety Population	Prior to first dose of randomized IP (or Visit 8 date if the dose date is missing) and after the first dose of open-label insulin lispro (or Visit 2 date if the dose date is missing)	From first dose of randomized IP to last dose of randomized IP AND From first dose of randomized IP to Visit 801
Hypoglycemia events	All Double-Blind Patients in the Safety Population	Visits 2-8	Visits 9-22 prior to discontinuation of IP
Weight and vital signs	All Double-Blind Patients in the Safety Population	Last of Visits 2-8	Visits 9-22 prior to discontinuation of IP AND Visits 9-801 regardless of IP use
Anti-insulin lispro antibody	All Double-Blind Patients in the Safety Population	Visit 2	Visits 3-801 regardless of IP use

Abbreviations: 1,5-AG = 1,5-Anhydroglucitol; ANCOVA = analysis of covariance; CCI [REDACTED]; HbA1c = hemoglobin A1c; IP = investigational product; ITSQ = Insulin Treatment Satisfaction Questionnaire; ITT = intention-to-treat; LOCF = last-observation-carried forward; MMTT = mixed meal tolerance test; MMRM = mixed-effect model repeated measures; SMBG = self-monitored blood glucose; TEAE = treatment-emergent adverse event CCI [REDACTED]

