10.2. Populations for Analyses

For purposes of analysis, the following populations are defined:

Population	Description
Entered	All patients who give informed consent.
Enrolled	All patients who receive at least 1 dose of open-label insulin lispro in the 8-week lead-in period.
Randomized	All patients who are randomly assigned to study treatment at Visit 8. Treatment group will be defined on the basis of the treatment the patients are assigned.
Safety	All randomized patients who receive at least 1 dose of the randomly assigned IP.
Completer	Patients included in the randomized population who have completed Week 26 of study treatment without permanent discontinuation of IP.
Per Protocol	Patients included in the randomized population who have completed Week 26 of study treatment without permanent discontinuation of IP and without significant protocol deviations through Week 26 that would significantly impact the primary objective. Treatment group will be defined on the basis of the treatment the patients actually receive.

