Eligibility	Inclusion/ Exclusion	Hematological conditions	Mixed (monitoring and clinical database)	CRF Pre-existing Conditions panel data using MedDRA terms that are considered as relevant hematological conditions by the CRP/CRS to indicate not compliant with entry criteria #25 Also identified by CRA as captured in sCTMS.
Eligibility	Inclusion/ Exclusion	Previous noninsulin antihyperglycemic medications	Mixed (monitoring and clinical database)	CRF Prior Diabetes Therapies / Concomitant Therapy panel data to indicate not compliant with entry criteria #32. Also identified by CRA as captured in sCTMS.
Eligibility	Inclusion/ Exclusion	Previous insulin therapy	Mixed (monitoring and clinical database)	CRF Prior Diabetes Therapies / Concomitant Therapy panel data to indicate not compliant with entry criteria #3, #4, #29, #30, #31. Also identified by CRA as captured in sCTMS.
Investigational Product	Treatment Assignment/ Randomization Error		Mixed (monitoring and clinical database)	IWRS data entry errors that impact patient stratification, for example, lab data indicated different strata from IWRS stratification report. Dispensing error: Patient was assigned to a treatment, but site gave a different treatment to the patient.
Investigational Product	Unblinding		Non Programmable (monitoring)	Any inadvertent unblinding affecting, patients, investigator, or sponsor.
Investigational Product	Patient Took Medication Not Fit for Use		Non Programmable (monitoring)	Study Drug not fit for use administered to patient.
Investigational Product	Other	Use of expired CT material	Non Programmable (monitoring)	Also identified by CRA as captured in sCTMS.

Description of Important Protocol Deviations

Category	Sub-categories	Description	Source	Methods of Identification
Study Procedures	Violation of Discontinuation Criteria		Mixed (monitoring and clinical database)	Patients not discontinued from treatment and/or study despite having met protocol specified discontinuation criteria. Also identified by CRA as captured in sCTMS Protocol Section 8.
Study Procedures	Excluded Conmeds		Mixed (monitoring and clinical database)	CRF Prior Diabetes Therapies / Concomitant Therapy panel data to indicate not compliant with entry criteria #28 and study-specific restriction on concomitant therapies Table ITRM.8 in the study protocol. Also identified by CRA as captured in sCTMS.

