6.12.3. Deaths

The listing of all deaths by patient for all enrolled patients will be provided as part of the SAE listing, regardless of the investigator's or the sponsor's judgment about causality. Each listing will include study ID, investigator ID, patient ID, treatment group, baseline age, sex, associated AE, first and last dose date for open label insulin lispro and randomized IP, and the event date.

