6.12.8. Patient Narratives

Patient narratives will be provided for all patients in the study who experience any of the following “notable” events prior to data cutoff for the submission:

- deaths
- serious adverse events
- discontinuations from study (or study drug) due to AEs
- pregnancy

A list of patients who meet the criteria for narratives will be provided.

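### The Safety population is entered and grouped by assigned product, so a patient mis-dispensed the other study insulin is left out of the main comparative safety tables or partly misclassified in them

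*SAP*

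**What the plan says.** Protocol 10.2 admits to the Safety population "All randomized patients who receive at least 1 dose of the randomly assigned IP" and gives no rule for which arm such a patient counts in. SAP Table 6.1 repeats the entry condition, "All randomized patients who receive at least 1 dose of the randomly assigned investigational product (IP"), and adds one: "Treatment group will be defined on the basis of the treatment the patients are assigned". SAP 6.1 makes this the default set: unless otherwise stated, "the safety analyses will be conducted on the Safety Population".

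The same table treats the Per Protocol set differently: "Treatment group will be defined on the basis of the treatment the patients actually receive".

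The SAP foresees mis-dispensing. Table 6.3 lists among the important protocol deviations: "Dispensing error: Patient was assigned to a treatment, but site gave a different treatment to the patient". The deviations that remove a patient from Per Protocol (SAP 6.9) concern consent, hematological conditions and missing HbA1c. A dispensing error is not among them.

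Some safety outputs use wider sets. On deaths, SAP 6.12.3 says: "The listing of all deaths by patient for all enrolled patients will be provided as part of the SAE listing". On narratives for deaths, SAEs, discontinuations due to AEs and pregnancy, SAP 6.12.8 says: "Patient narratives will be provided for all patients in the study". The hypoglycemia subgroup analyses (SAP 6.13.2) and the deviation listing (SAP 6.9) cover all randomised patients.

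**The concern.** A safety table is usually read as harm by the product patients were exposed to. Here both the entry condition and the grouping follow the assigned product. If a site dispenses the wrong pens, an exposed patient may be absent from the tables, or an event may appear under a product that was not in use when it began. The plan anticipates the error and already needs treatment received for Per Protocol, but does not carry it over to safety. A mis-dispensed patient could therefore appear under the received product in the Per Protocol HbA1c analysis and under the assigned product in the safety tables. Most exposed are rare outcomes such as severe hypoglycemia or systemic hypersensitivity, where one patient is visible in the comparison.

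**Working it through.** The documents give no figure for dispensing errors, so the first step is to follow the definitions through. No sample size, power or alpha depends on this point.

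**Step 1. Which outputs use the Safety set.** SAP Tables 6.2 and 6.5 name it for treatment-period TEAEs, hypoglycemia, laboratory tests, weight and vital signs, and anti-insulin lispro antibodies. The wider-set outputs are the four named above.

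**Step 2. Three kinds of mis-dispensed patient.**
- *Only the other insulin, never the assigned one.* Fails the entry condition and is absent from the Step 1 tables. Still reached by the four wider-set outputs.
- *Some doses of each.* Enters the Safety set under the assigned arm. Only events arising while on the wrong pens are misattributed.
- *LY900014 and LY900014+20 confused.* Same product, so product attribution is correct. The error is in timing and blinding, and grouping by product received does not settle the arm.

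**Step 3. Weight of one patient.** Planned arms (Protocol 10.1): 436 + 436 + 327 = 1199, as stated.
- Patient with the event: 1/436 = 0.23 percentage points in a double-blind arm; 1/327 = 0.31 in the open-label arm.
- Event-free patient dropped, assuming 13 events (about 3%): 13/436 = 2.982% and 13/435 = 2.989%, a change of about 0.007 points.

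**Step 4. Mixed exposure.** Assume a share m of each double-blind arm spends a fraction f of its exposure on the other blinded product, with constant event rates r1 and r0.
- Arm 1 as assigned: (1 − mf)r1 + mf·r0
- Arm 0 as assigned: (1 − mf)r0 + mf·r1
- Observed difference: (1 − 2mf)(r1 − r0)

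The Schedule of Activities dispenses IP at Weeks 0, 4, 8, 12, 18 and 22 before Week 26. One wrong dispensing therefore covers 4/26 = 0.15 to 6/26 = 0.23 of the period.
- f = 0.23, with m assumed at 1%, 2% or 5%: difference multiplied by 0.995, 0.991 or 0.977.
- Ceiling, f close to 1 (one assigned dose, otherwise all wrong): 0.98, 0.96 or 0.90. An assumed true difference of 5.0 points would show as 4.90, 4.80 or 4.50.

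These values of m mean about 4.4, 8.7 and 21.8 patients per arm of 436. They are assumptions chosen to show a range. A patient at exactly f = 1 has left the Safety set and contributes no attenuation.

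**Step 5. The TEAE window.** Table 6.2 opens the treatment-period window at the first dose of randomised IP and counts the time before it, back to the first lead-in lispro dose, as baseline. If that is read as the assigned product and the wrong pens came first, events on them would fall into baseline. SAP 6.12.2 uses broader wording that would include them. The two should agree.

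**The case against.** Grouping by assignment is explicit and prespecified, and it keeps the randomised comparison. The protocol is silent on Safety grouping, and both documents let the SAP add such detail, so they do not contradict each other. Errors should be few: the IWRS assigns all IP, and the site must enter a pen confirmation number (Protocol 7.2). Complete exclusion needs a wrong dispensing every time, or a stop before any correct pen is used. Serious harms and mis-dispensed patients remain visible through the wider-set outputs. For mixed exposure, a rule based on longest exposure would usually return the patient to the assigned arm, so regrouping would change little.

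Most of this stands, and it limits the size of the point. It does not explain why a patient exposed only to the other study insulin should be missing from the comparative tables. Preserving randomisation is no argument for the entry condition, which itself removes randomised, dosed patients. The remark on mixed exposure is also right, which is why the event-level listing in the fix matters more than the regrouping.

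**Conclusion.** The point holds as a gap in the Safety definition that is cheap to close and has a small expected effect. It rests on a literal reading of Table 6.1 and on the absence of any as-received safety analysis in the SAP. The size cannot be estimated, because no error rate is given; the working shows a range under stated assumptions only.

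Three stronger readings are tempting and not supported:
- *That mis-dispensed patients vanish from every safety analysis.* They do not; four outputs use wider sets.
- *That both features pull safety comparisons toward no difference.* Only misattribution under mixed exposure does so. Excluding a patient who took only the other product loses information, but its direction is unknown.
- *That the dilution can be sized by supposing a share of each arm took the other product throughout.* Those patients never took the assigned product, so the entry condition keeps them out and they cannot dilute the as-assigned contrast.

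**What to change.** - **Entry (SAP Table 6.1, with Protocol 10.2 aligned).** Safety becomes all randomised patients with one or more doses of either study prandial insulin (LY900014 or insulin lispro) supplied for the randomised period.
- **Grouping.** Use treatment actually received, with a stated rule for mixed exposure: for example, the assigned arm if any assigned product was taken, otherwise the product received. Under that rule mixed-exposure patients stay in the assigned arm, so the listing below must carry the attribution. State separately where LY900014 and LY900014+20 mix-ups count.
- **Listing.** List every mis-dispensed patient with all events and the product in use at onset.
- **TEAE start (SAP Table 6.2).** Use the first dose of any randomised-period study insulin, consistent with SAP 6.12.2.

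Cost: SAP wording and one derived variable. Per Protocol already needs treatment received for its members; the derivation is extended to all dosed patients. Protocol 10.3.1 and SAP 6.1 require an amendment only for a change to a principal feature, so recording the change and its justification in the SAP may suffice. Downside: safety denominators may differ from the randomised counts by a few patients.
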